11.5.2. Control Arm- AAD Initiation

Subjects must initiate a Class I or III AAD within 30 days of randomization. It is recommended that AADs be initiated as soon as possible after randomization, with a target of within 14 days. The investigator should choose the appropriate AAD per his or her standard of care; however, amiodarone should only be used if other AADs were not tolerated or failed. The 2014 AHA/ACC/HRS Guideline for the Management of Patients with AF should be consulted for AAD prescriptions. Modifications to AADs (type or dosage increase) may be made for up to 90 days after AAD initiation. This is referred to as the AAD optimization

period. Dosing of AADs can be individually tailored until the end of the AAD optimization period. After the optimization period, further AAD therapy optimization or change should be avoided or at least allowed only up to physicians' discretion to guarantee the safety of the patients. The possible concomitant use of beta blockers can still be optimized after the optimization period. Reason for AAD modification must be documented.

Crossovers from AAD therapy to cryoablation will be allowed only if the subject in the control group is deemed a treatment failure. Crossovers must be pre-approved by the Medtronic Clinical Study Manager. Approval will be granted after verification that the subject is an efficacy failure.

Treatment failure is defined in section 5.1.4.1.

11.5.3. Treatment Arm- Cryoablation Procedure

Within 30 days of randomization, perform the pulmonary vein isolation procedure using the Arctic Front Advance™ Cardiac CryoAblation Catheter.

If needed, a Freezor® MAX Cardiac CryoAblation Catheter may also be utilized for gap ablation to complete electrical isolation of the pulmonary veins and creation of ablation lines between the inferior vena cava and the tricuspid valve. The Investigator is to perform the procedure according to the procedural steps in this CIP and the Instructions for Use for the catheters. Appropriate sedation and venous access should be attained at the Investigator's standard practice according to their institution's pre-established procedures/guidelines at the time of the procedure.

The use of any non-study device in the left atrium is not permitted.

Only the Medtronic FlexCath sheath family should be used with the Arctic Front Advance™ Cardiac CryoAblation Catheter. The use of other sheaths may damage the device. The Investigator may choose compatible guidewires and mapping catheters at his or her discretion.

11.5.3.1. Esophageal Visualization and Temperature Monitoring

Ensure an esophageal temperature monitor is used for each cryoablation application. The cryoapplication must be ceased if the temperature reaches $\leq 15^{\circ}\text{C}$.

11.5.3.2. Pre-procedure Anticoagulation

Current recommendations for anticoagulation are found in the 2017 HRS/EHRA/ECAS Expert Consensus Statement on Catheter and Surgical Ablation of Atrial Fibrillation (Calkins, et. al. 2017). Anticoagulation pre-procedure should be determined based upon the subjects CHA₂DS₂-VASc score. Oral anticoagulants are required if the subject has had a prior stroke or TIA, or if the subject has a CHA₂DS₂-VASc score ≥ 2 . When anticoagulation is required, subjects must take it for at least 21 days prior to an ablation procedure. Oral anticoagulants are not required for subjects with nonvalvular AF and a CHA₂DS₂-VASc score of 0 or 1.

11.5.3.3. Intra-procedure Anticoagulation

Heparin should be administered prior to or immediately following transseptal puncture during AF ablation procedures and adjusted to achieve and maintain an ACT of 300-400 during the procedure, with ACT recommended to be checked at 30 minutes intervals. Administration of protamine following ablation to reverse heparin should be considered.

11.5.3.4. Post-procedure Anticoagulation

Systemic oral anticoagulation should be initiated on the day of the procedure and is recommended for at least two months following an AF ablation procedure. Decisions regarding the continuation of systemic anticoagulation agents more than two months following ablation should be based on the patient's risk factors for stroke as estimated by the CHA₂DS₂-VASc score and not on the presence or type of AF.

Discontinuation of systemic anticoagulation therapy post ablation is not recommended in patients who are at high risk of stroke as estimated by the CHA₂DS₂-VASc score.

11.5.3.5. Diaphragm Movement

- a. Prior to the first cryoablation application, the Investigator will make a fluoroscopic recording of inspiratory and expiratory movement of the diaphragm.
- b. Continuous phrenic nerve pacing with abdominal palpitation must be performed for all right pulmonary vein cryoapplications and should be considered for all cryoapplications. Additional methods of phrenic nerve monitoring are encouraged, such as diaphragmatic compound motor action potential (CMAP).
- c. After the last cryoablation application, the Investigator will make a fluoroscopic recording of inspiratory and expiratory movement of the diaphragm.

11.5.3.6. Balloon Pulmonary Vein (PV) Cryoablation

- a. Every effort consistent with subject welfare will be made to treat all PVs or their anomalous equivalents.
- b. The catheter will be advanced into the left atrium over the mapping catheter or guidewire and inflated. Once inflated, the catheter will be tracked over the Achieve™ catheter and positioned at the entrance of the PV.
- c. Assess the positioning, contact and occlusion of the PV by the catheter's balloon by injection of contrast material, ultrasound imaging, or other technique. Reposition as needed.
- d. Each pulmonary vein must be assessed for entrance block and, where assessable, exit block to demonstrate electrical isolation.
- e. It is recommended that the Investigator use cryoapplications of three (3) minutes each. Once PV isolation has been achieved, one (1) additional application of three (3) minutes at the same PV should be performed; however, it is up to the operator's discretion to assess application time and necessity of the additional freeze given factors such as time to isolation of prior application(s), temperature of prior application(s), risk of collateral damage, etc.
- f. Upon the Investigator's assessment of procedure completion, isoproterenol and/or adenosine may be used to assess pulmonary vein isolation.

11.5.3.7. Other Ablations During Index Procedure

- a. Ablation of the cavotricuspid isthmus is required in subjects with a history of typical atrial flutter or inducible cavotricuspid isthmus dependent atrial flutter. Complete an assessment for bi-directional block if this procedure is performed. Any commercially released catheter deemed appropriate for the procedure may be used.

- b. The following are not allowed:
 - Left atrial non-PVI ablations including but not limited to, ablation of linear lesions, complex fractionated electrograms or non-PV triggers
 - Ablation using any non-study device in the left atrium

11.5.3.8. Cardioversion

- a. Electrical or pharmacological cardioversion to sinus rhythm must be attempted following the PVI portion of the procedure if sinus rhythm wasn't restored. Cardioversion may be performed prior to PVI if needed.

11.5.3.9. Procedure Documentation

During the procedure the investigator will document the following:

- Catheters used (i.e. Arctic Front Advance™, Freezor® MAX and Achieve™ Mapping Catheter, etc.)
- Minimum temperature for each cryoapplication
- Duration of each cryoapplication
- Vein location for each cryoapplication (e.g. right superior PV)
- Use of phrenic nerve pacing or other phrenic nerve monitoring technique for each cryoapplication, specifically those cryoapplications surrounding the RS and RI PVs
- Demonstrated electrical block and, if real-time signals are available, time to isolation
- Adjunctive catheters, mapping or visualization devices, sedation type, procedure information, esophageal temperature, ACT, cardioversion use and fluoroscopy time will be collected.

11.5.4. Hospital Discharge

At or shortly before hospital discharge, the following will be performed and collected:

- Adverse event assessment
- In the case of suspected PV stenosis, Magnetic Resonance Imaging (MRI) or Computerized Tomography Scanning (CT scan) is required.
- Review medications
- 12 lead ECG
- Chest X-ray: For any subject whose post-procedural fluoroscopy demonstrated study-related PNI, a follow-up chest X-ray, including inspiration and expiration films, will be performed
- Review study requirements with the subject to help ensure compliance with follow-up procedures
- Evaluate the subject's neurological status per institutional standard of care to determine if a formal neurological consultation should be performed for stroke assessment. Report any adverse events that result from the neurologic evaluation and consultation, if applicable.

11.5.5. Medication Compliance

Information regarding medications prescribed for anticoagulation or to treat atrial arrhythmias will be collected through study exit. The following information will be collected for medications to treat atrial arrhythmias: medication name, purpose for use, start and stop dates, dose, dosage changes (and reasons for changes), and route of administration. Data collection for anticoagulation medication will be limited to medication name and start and stop dates.

Control Arm (AAD):

Subjects must initiate a Class I or III AAD within 30 days of randomization. It is recommended that AADs be initiated as soon as possible after randomization, with a target of within 14 days. The investigator should choose the appropriate AAD per his or her standard of care; however, amiodarone should only be used if other AADs were not tolerated or failed. The 2014 AHA/ACC/HRS Guideline for the Management of Patients with AF should be consulted for AAD prescriptions. Modifications to AADs (type or dosage increase) may be made for up to 90 days after AAD initiation. This is referred to as the AAD optimization period. Dosing of AADs can be individually tailored until the end of the AAD optimization period. After the optimization period, further AAD therapy optimization or change should be avoided or at least allowed only up to physicians' discretion to guarantee the safety of the patients. The possible concomitant use of beta blockers can still be optimized after the optimization period.

Cryoablation (Treatment Arm):

Per physician discretion, class I or III antiarrhythmic, including sotalol, medication use is permitted for up to 80 days following the ablation procedure. Use of amiodarone is not permitted. Prescriptions for these drugs must not allow a quantity that will last longer than 80 days post-procedure. It is recommended that site personnel contact subjects on day 80 post-ablation procedure to ensure they have stopped taking class I or III antiarrhythmic drugs. Class I or III antiarrhythmic drug use after the 90 day blanking period will be considered a primary endpoint failure.

Systemic oral anticoagulation should be initiated on the day of the procedure and is recommended for at least two months following an AF ablation procedure. Decisions regarding the continuation of systemic anticoagulation agents more than two months following ablation should be based on the patient's risk factors for stroke as estimated by the CHA₂DS₂-VASc score and not on the presence or type of AF.

Discontinuation of systemic anticoagulation therapy post ablation is not recommended in patients who are at high risk of stroke as estimated by the CHA₂DS₂-VASc score.

All Subjects:

All other medications (those that are not specified above) are permitted in the study, with the exception of investigational drugs that may confound the study results. Beta-blockers may be prescribed per standard of care.

11.5.6. Subsequent Ablation Procedures

Any subsequent ablation in the left atrium or AF surgery will be counted as an endpoint failure. There is no 90 day blanking period for repeat ablation. Subsequent ablations and AF surgeries will be documented on an eCRF.

Subsequent ablations in the right atrium are allowed (e.g. typical atrial flutter ablation).

11.5.7. Cardioversions

Electrically and pharmacologically cardioverting the subject to sinus rhythm is allowed in the 90 day post-procedure blanking period (treatment arm)/AAD optimization period (control arm) at the discretion of the Investigator. Electrically or pharmacologically cardioverting the subject to sinus rhythm after the blanking period/AAD optimization period will be counted as an efficacy endpoint failure.

11.5.8. Scheduled Follow-up Visits

After the index cryoablation procedure (treatment arm) or AAD initiation (control arm) is reported in the study database, the database will calculate the target dates and windows for each visit to the site. Should a subject miss a visit or the visit fall outside the pre-specified window, a study deviation must be reported and the original follow-up schedule maintained for subsequent visits.

Data analyses include follow-up visits, regardless of whether the visit occurs within the window. Therefore, a late visit is preferred over a missed visit but must be accompanied by a deviation. Follow-up visit windows are listed in Table 6 and are based on days post-index procedure or AAD initiation.

Table 6: Follow-up Visit Windows

| Occurrence/ Visit | Window (Calculated days post-procedure or AAD initiation) | |
|---|---|------------|
| | Window Start | Window End |
| Randomization | -30 days | Day 0 |
| Index Cryoablation Procedure/ AAD initiation | Day 0 | Day 0 |
| 1 month | 31 days | 51 days |
| 3 month | 91 days | 111 days |
| 6 month | 165 days | 195 days |
| 12 month | 365 days | 395 days |

The following activities will occur at the follow-up visits:

11.5.8.1. One Month Office Visit

- Review medications
- Adverse event assessment
- Review symptoms suggestive of recurrent AF/AT/AFL
- Health care utilization assessment- collect information about hospitalizations or emergency department visits experienced by the subject since the last visit
- 12 lead ECG
- Chest X-ray
 - For any subject whose post-procedural fluoroscopy demonstrated study-related PNI, a follow-up chest X-ray, including inspiration and expiration films, will be performed if the PNI was unresolved at hospital discharge.
- In the case of suspected PV stenosis, Magnetic Resonance Imaging (MRI) or Computerized Tomography Scanning (CT scan) is required. It is not required at this visit if it was already completed at an earlier visit and PV stenosis was confirmed.

11.5.8.2. Three Month Visit

- Review medications
- Adverse event assessment
- Review symptoms suggestive of recurrent AF/AT/AFL
- Health care utilization assessment- collect information about hospitalizations or emergency department visits experienced by the subject since the last visit
- 12 lead ECG
- Provide the subject with patient-activated ambulatory monitoring equipment; provide instructions for and weekly and symptomatic transmissions.
- Chest X-ray
 - For any subject whose post-procedural fluoroscopy demonstrated study-related PNI, a follow-up chest X-ray, including inspiration and expiration films, will be performed if the PNI was unresolved at the one month visit
- In the case of suspected PV stenosis, Magnetic Resonance Imaging (MRI) or Computerized Tomography Scanning (CT scan) is required. It is not required at this visit if it was already completed at an earlier visit and PV stenosis was confirmed.

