5.1.4. Primary Endpoint

5.1.4.1. Primary Efficacy Endpoint

The primary endpoint is treatment success at 12 months after AAD initiation (control arm) or after the pulmonary vein isolation ablation procedure utilizing the Arctic Front Advance™ Cardiac CryoAblation Catheter (treatment arm). A treatment success is the opposite of a treatment failure.

Treatment failure is defined as any of the following components:

- a) Acute procedural failure (treatment arm only)
- b) Documented AF/AT/AFL on ambulatory monitoring/12-lead ECG after the 90 day post-ablation blanking period (treatment arm)/AAD optimization period (control arm).
 - o Minimum of 30 seconds on ambulatory monitoring or 10 seconds on 12-lead ECG.
 - o Note: Documented occurrence and treatment of typical right-sided cavotricuspid isthmus dependent atrial flutter is not considered a failure if confirmed by entrainment maneuvers during EP testing.
- c) Any subsequent AF surgery or ablation in the left atrium.
- d) Any subsequent cardioversion after the 90 day post-ablation blanking period (treatment arm)/AAD optimization period (control arm).
- e) Class I or III antiarrhythmic drug (or sotalol) use after the 90 day blanking period (treatment arm only).

The AAD optimization period is defined as the first 90 days after AAD initiation (control arm). The post-ablation blanking period is defined as the first 90 days after the index ablation procedure (treatment arm). Recurrences of atrial arrhythmias during the AAD optimization/blanking periods will not be counted in the determination of the first clinical failure for the primary endpoint.

Within the AAD optimization period/post-ablation blanking period, recurrent arrhythmias can be managed with medications or cardioversions. Reablation will be considered a primary endpoint failure at all times, including during the 90 day post-ablation blanking period.

Acute procedural failure (treatment arm only) is defined as:

- a) Inability to isolate all accessible targeted pulmonary veins (assessed for entrance block and, where assessable, exit block) during the index ablation procedure.
- b) Left atrial non-PVI ablations including but not limited to, ablation of linear lesions
- c) Use of a non-study device in the left atrium.

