11.1.1. Modes of Data Collection

Multiple modes of data collection may be employed to support the collection of required visit data at the 3 and 6 month visits. This includes such methods as:

- In-office patient clinic visit
- Direct to patient contact (i.e. telephone, email, mail contact, etc.)
- Remote technology transmissions/uploads

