11.2. Medications

Information regarding drugs prescribed to treat atrial arrhythmias will be collected, including the purpose for their use/reason for modification, and start and stop dates. Information regarding anticoagulation medications will be collected, including start and stop dates.

Control Arm (AAD): Subjects must initiate a Class I or III AAD within 30 days of randomization. It is recommended that AADs be initiated as soon as possible after randomization, with a target of within 14 days. The investigator should choose the appropriate AAD per his or her standard of care; however, amiodarone should only be used if other AADs were not tolerated or failed. The 2014 AHA/ACC/HRS

⁴ Subjects shall submit ECG transmissions weekly and whenever symptoms occur after the AAD optimization/post-ablation blanking periods through 12 month follow-up.

Guideline for the Management of Patients with AF should be consulted for AAD prescriptions. Modifications to AADs (type or dosage increase) may be made for up to 90 days after AAD initiation. This is referred to as the AAD optimization period. Dosing of AADs can be individually tailored until the end of the AAD optimization period. After the optimization period, further AAD therapy optimization or change should be avoided or at least allowed only up to physicians' discretion to guarantee the safety of the patients. The possible concomitant use of beta blockers can still be optimized after the optimization period.

Treatment Arm (Cryoablation): Subjects may be prescribed Class I or III AADs for up to 80 days post-ablation procedure at the discretion of the Investigator. Subjects must stop taking all Class I or III AADs before day 81 post-ablation. Use of amiodarone is not permitted.

Anticoagulation requirements for all subjects:

Anticoagulation pre-procedure should be determined based upon the subjects CHA₂DS₂-VASc score.

- a. Oral anticoagulants are required if the subject has had a prior stroke or TIA, or if the subject has a CHA₂DS₂-VASc score ≥ 2 . When anticoagulation is required, subjects must take it for at least 21 days prior to an ablation procedure.
- b. Oral anticoagulants are not required for subjects with nonvalvular AF and a CHA₂DS₂-VASc score of 0 or 1.

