11.5.12. Ambulatory Monitoring

Market- released ambulatory monitoring equipment will be distributed by a core lab to centers after activation has occurred. Subjects will be provided with a small patient-activated electronic ambulatory

monitoring device after the AAD optimization (control arm) or post-ablation blanking period (treatment arm) ends. This device will serve two functions:

- 24 hour continuous monitoring: This is traditionally done using a Holter monitor. The investigative site personnel will apply the device patches for the subject during the subject's 6 month visit and train the subject how to apply the device. The subject will be asked to apply the continuous monitoring patches themselves prior to the 12 month study visit. Additionally, subjects may be asked to perform 24 hour continuous monitoring on their own if they miss a scheduled study visit.
- Patient-activated mode: Subjects will be asked to transmit ECG data weekly and whenever they experience AF symptoms. This mode does not require adhesive patches; the subject simply holds the device to his or her chest for a short period of time.

In both modes, the data automatically transmits to the core lab via a secured cell phone connection.

The core lab will manage maintenance, calibration and tracking of the ambulatory monitoring equipment. The core lab will be responsible for adjudication of rhythm documentation for the primary efficacy objective of the study. The core lab will send the results of all ambulatory monitoring analyses to the Investigators for appropriate follow-up, if necessary, and assessment for adverse event reporting.

Subjects will return the ambulatory monitoring equipment at the 12 month follow-up visit.

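### Arrhythmia counts as failure from day 91, but the monitor is supplied only at a 3-month visit on days 91-111, leaving 0-20 endpoint days without scheduled or handheld recording

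*Protocol*

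**What the plan says.** **Start of endpoint counting.** Protocol 5.1.4.1: "The post-ablation blanking period is defined as the first 90 days after the index ablation procedure (treatment arm"), and "The AAD optimization period is defined as the first 90 days after AAD initiation (control arm"). Documented AF/AT/AFL after that point is a failure in either arm.

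**Start of transmissions.** Footnote 4 to Table 5 in the protocol: "Subjects shall submit ECG transmissions weekly and whenever symptoms occur after the AAD optimization/post-ablation blanking periods through 12 month follow-up".

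**Supply of the device.** Section 11.5.12 gives subjects the "monitoring device after the AAD optimization (control arm) or post-ablation blanking period (treatment arm) ends". Section 11.5.8.2 places this at the 3-month visit: "Provide the subject with patient-activated ambulatory monitoring equipment". The window in Table 6 is "3 month | 91 days | 111 days". Section 11.5.8 prefers a late visit to a missed one, with a deviation report.

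**Remote visits.** Section 11.1.1: "Multiple modes of data collection may be employed to support the collection of required visit data at the 3 and 6 month visits". The listed modes include telephone, email, mail and uploads. Yet 11.5.12 sends the equipment from the core lab to the centers, and says that at 6 months "investigative site personnel will apply the device patches for the subject during" the visit. No route to a subject seen remotely is described, and no latest date for supply is set.

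**The concern.** Footnote 4 cannot be met by any subject whose 3-month visit falls after day 91, because that subject does not yet hold the device. Between day 91 and the visit the protocol schedules no rhythm recording, so an episode that does not lead to an unscheduled visit or an intervention goes undocumented and the subject stays event-free in the Kaplan-Meier analysis.

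Two things are at stake. The first is sensitivity: some early recurrences are found late or not at all. The second is comparability: the trial is unblinded, nothing fixes the visit date within days 91-111 or the visit mode, and missed transmissions need no deviation report (11.9). The plan does not ask for the first-transmission day by arm, so a difference between arms could go unreported. Protocol 6.2 also supports its control-arm assumption by pointing to similar transmission monitoring in the earlier first-line radiofrequency trial, so the start of monitoring should be firm.

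**Working it through.** **Inputs.** Blanking or optimization ends on day 90 (protocol 5.1.4.1). The analysis runs to day 365 (15.1.5). The 3-month window is days 91-111 (Table 6). Success rates are 69.9% and 45.9%, by two-sided Pearson chi-square at alpha 0.05 (SAP 7.1). There are 94 analysed per arm, from 210 randomized less 10% attrition (SAP 7.2).

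**The plan's own figure.** With p1 = 0.699, p2 = 0.459 and n = 87 per arm, power = Φ((d − 1.96·SE0)/SE1), where d = p1 − p2, SE0 = √(2·p̄(1−p̄)/n) and SE1 = √((p1(1−p1) + p2(1−p2))/n). This gives 90.05%, matching the SAP's 174 subjects and 0.901; 174/0.9 rounds up to 194.

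**Length of the gap.** Endpoint days are 91-365: 365 − 90 = 275, or 275/7 = 39.3 weeks. Gap = visit day − 91.

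| 3-month visit | Gap (days) | Share of 275 | Weekly slots lost |
|---|---|---|---|
| day 91 | 0 | 0% | 0 |
| day 98 | 7 | 2.5% | 1.0 |
| day 105 | 14 | 5.1% | 2.0 |
| day 111 | 20 | 7.3% | 2.9 |
| day 125 (late, deviation) | 34 | 12.4% | 4.9 |

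**Upper bound on first failures in the gap.** Assume that every composite failure is an arrhythmia after day 90 and that the hazard is constant. The documents give no hazard shape.
- Drug arm: h = −ln(0.459)/275 = 0.00283 per day; 1 − exp(−20h) = 5.5% (2.8% for 10 days).
- Cryoablation arm: h = −ln(0.699)/275 = 0.00130 per day; 1 − exp(−20h) = 2.6% (1.3% for 10 days).

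**Equal 20-day gap, every gap event lost for good.** Observed success = p^(1 − 20/275): 0.699 becomes 0.717 and 0.459 becomes 0.486. The difference falls from 24.0 to 23.2 points. With n = 94:
- No gap: SE0 = 0.0720, SE1 = 0.0699, Φ((0.240 − 0.1412)/0.0699) = 92.1%.
- Gap: SE0 = 0.0714, SE1 = 0.0694, Φ((0.2317 − 0.1400)/0.0694) = 90.7%.

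**Gap in one arm only (hypothetical), same assumptions.**
- Drug arm only: 0.699 − 0.486 = 21.3 points, power 85.1%.
- Cryoablation arm only: 0.717 − 0.459 = 25.8 points.
- No true effect, 20-day gap in one arm: spurious difference 1.8 points (true success 69.9%) to 2.7 points (45.9%); two-sided rejection 5.9% to 6.5% instead of 5%.

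**Sensitivity to hazard shape.** If the hazard in the gap is k times the later hazard, the exponent becomes 1 − 20k/(20k + 255). For k = 2 and 3 (assumed values), the equal-gap power is 89.2% and 87.6%. The spurious difference from a full gap in one arm alone is 3.5-5.1 points for k = 2 and 4.9-7.3 points for k = 3.

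**The case against.** The case for leaving the plan alone has real force, and four parts of it stand.

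- **The period is not wholly unmonitored.** Section 11.5.9 requires a 12-lead ECG at unscheduled cardiovascular visits and sends it to the core lab. Cardioversion, left-atrial ablation and, in the cryoablation arm, class I or III drug use still count as failures. The 12-lead ECG at the 3-month visit itself falls in the endpoint period.
- **Remote visits waive nothing.** A reader might infer that a subject seen remotely has no 12-lead ECG at 3 or 6 months and no 24-hour recording. Section 11.1.1 does not say so. The tests stay on the schedule, and omitting one would be a deviation. Mailing a device is unstated but not excluded, and 11.5.12 already foresees self-applied 24-hour recording when a visit is missed. What is missing is a description of how a remote subject receives the device and completes these tests.
- **Arm-dependent detection is not shown.** A reader might infer that unblinded sites control the gap and that this favours ablation. The windows are the same in both arms and calculated by the database, the subject also influences the date, and an independent core lab adjudicates rhythm. Nothing in the documents indicates which arm would be seen later or remotely more often.
- **The size is a ceiling.** The hazards treat acute procedural failure and other non-rhythm components as post-blanking arrhythmia, and later recordings would catch many of the missed recurrences. An equal gap slightly narrows the difference, so it does not favour the device.

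None of this removes the mismatch between footnote 4 and the supply of the device.

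**Conclusion.** The inconsistency is real: transmissions are required from the end of day 90, but the device cannot be supplied before then and may arrive up to 20 days later within the window, or later still with a deviation. The loss is at most 7.3% of endpoint days for an in-window visit, and zero for a visit on day 91.

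With equal gaps the cost is small. Power stays above 90% under a constant hazard even if every gap event is lost, because the safety endpoint sets the sample size and leaves some margin. It falls slightly below 90% only if the early hazard is assumed to be two to three times the later one. The sample size need not change.

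Bias requires visit date or mode to differ between arms. The documents do not show that this will happen; they only fail to prevent it or to plan a report that would reveal it. This is a cheap improvement to the protocol, not a flaw that undermines the primary comparison.

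**What to change.** 1. Amend 11.5.12 and 11.5.8.2 together, so that the device is with the subject and training is done by day 90. It can be handed over at the 1-month office visit or shipped shortly before day 90. The first transmission is then due on day 91. Changing 11.5.8.2 alone would leave the sentence in 11.5.12 that ties supply to the end of the 90 days.
2. State that the device is not used for study transmissions before day 91. Core-lab results go to the investigators, so earlier recordings would reach unblinded sites during blanking, while control-arm drugs may still be changed.
3. State in 11.1.1 that the 12-lead ECG and the 6-month 24-hour recording remain required when the 3- or 6-month visit is remote, with the 24-hour recording self-applied as at 12 months.
4. Add to the SAP a table by arm of visit mode, day of first transmission and transmission compliance.

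Cost: protocol and SAP wording, with no new visit. Each device is out longer. Moving supply from days 91-111 to the 1-month window of days 31-51 adds 40 days (91 − 51) to 80 days (111 − 31), about 6 to 11 weeks; shipping near day 90 adds less.
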